##### B. Determination of Subject s/Data for Analysis

The population(s) used for descriptive summarization will be the mITT set.

### 3.3.4 Secondary Objective #4(Cryoablation)

Cryoablation procedure parameters will be summarized

#### 3.3.4.1 Hypothesis

There is no hypothesis.

#### 3.3.4.2 Endpoint Definition

- Cryoablation procedure parameters such as total number of cryoablation attempts, mean number of cryoablation attempts per attempted subject and number of successful cryoablations per subject will be summarized using descriptive statistics.
- Cryoablation temperature and ablation procedure time (duration) will be summarized using descriptive statistics.

#### 3.3.4.3 Analysis Methods

##### A. Statistical Methodology

Tables and descriptive statistics will be used to summarize subject data with respect to these variables. For quantitative variables, number of nonmissing observations, mean, median, minimum, maximum and standard deviation will be calculated. For qualitative variables, percentages and counts will be calculated. Summaries for index ablation and re-treatment procedures will be reported separately. Categories of 'other' will be reported in associated listings.

For the final report, most of the statistics reported will describe subject level phenomena, requiring aggregation (for example, by taking the average, minimum or maximum) when measurements such as cryoablation temperature are recorded in the data at the patient or application level.

##### B Determination of Subject s/Data for Analysis

The population used for descriptive statistics will be the mITT set.

### 3.3.5 Secondary Objective #5(Procedure and Fluoroscopy Time)

Total procedure time and total fluoroscopy time will be summarized.

#### 3.3.5.1 Hypothesis

There is no hypothesis.

#### 3.3.5.2 Endpoint Definition

- Total procedure time defined as the period from puncture of the skin performed to obtain venous access for catheter placement to final ECG (electrocardiogram) at end of procedure will be analyzed using descriptive statistics.
- Total fluoroscopy time will be analyzed using descriptive statistics.

### 3.3.5.3 Analysis Methods

#### A. Statistical Methodology

Tables and descriptive statistics will be used to summarize subject data with respect to these variables. The number of nonmissing observations, mean, median, minimum, maximum and standard deviation will be calculated. Summaries for index ablation and re-treatment procedures will be reported separately.

#### B. Determination of Subjects/Data for Analysis

The population used for descriptive statistics will be the mITT set.

### 3.3.6 Secondary Objective #6 (Adverse Events/Other)

All adverse events will be summarized.

#### 3.3.6.1 Hypothesis

There is no hypothesis.

#### 3.3.6.2 Endpoint Definition

All adverse events that occur during the study will be captured on the CRFs.

#### 3.3.6.3 Analysis Methods

##### A. Statistical Methodology

All adverse events will be summarized by presenting the number of events, the number and percentage of subjects having any AE, having an AE in each body system, and having each individual AE. Any other information collected (e.g., seriousness, severity or relatedness to device/procedure) will be presented as appropriate.

##### B. Determination of Subjects/Data for Analysis

The population used for descriptive statistics will be the enrolled set. Summaries will be presented for both the Intent-To-Treat (ITT) Set and Modified Intent-To-Treat (mITT) Set.

### 3.4 Additional Analyses

#### 3.4.1 Additional Analysis Objective #1

Though not defined as an objective in the CIP, a posthoc analysis on SF-12 Health Survey scores collected at baseline, 6 month, 12 month, 2 year, and 3 year visits will be included in the Final Report.

### 3.4.1.1 Hypothesis

There is no formal statistical hypothesis associated with this objective.

### 3.4.1.2 Endpoint Definition

There are two endpoints associated with this objective: the SF-12 physical health component score and the SF-12 mental health component score.

### 3.4.1.3 Analysis Methods

#### A. Statistical Methodology

The Medical Outcome Study Short Form-12 (SF-12) questionnaire will also be utilized for this objective. The SF-12 questionnaire is a health-related quality of life questionnaire to evaluate the subject's mental and physical performance. For each questionnaire, the physical and mental component scores were calculated using standard scoring algorithms that combine the survey item responses. Both the physical and mental component scores range from 0 to 100, where a 0 score indicates the lowest level of health measured by the scale and 100 indicates the highest level of health.

Summary statistics (e.g. mean, SD, 95% confidence intervals) and graphical methods will be used to describe SF-12 scores from baseline through 36 months. For a subject's physical health score to be calculated at either time point, all physical health dimension questions must be answered; likewise, for mental health scores to be calculated, all mental health questions must be answered. Analysis will be performed on all complete questionnaires from subjects in the mITT dataset.

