## 4 APPENDIX

### 4.1 Overall Sample Size

In order to adequately power for both the primary effectiveness and safety hypotheses, we require a sample size of 270 evaluable subjects to complete 36 months of follow-up. We estimate that the attrition rate will be approximately 10% per year for the duration of the originally intended 5 year follow-up period. Therefore, the final sample size required to achieve 270 subjects followed for 36 months and account for attrition (i.e. 10% per year) is 370 mITT subjects with procedure attempts. It is expected up to 400 subjects will need to be enrolled to ensure 370 mITT subjects with procedure attempts assuming a small number of subjects who are enrolled will not undergo a procedure.

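### SF-12 is summarised visit by visit on a shrinking set of subjects, with no within-subject change, so its course from baseline to 36 months can mix change with dropout

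*SAP*

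**What the plan says.** SAP section 3.4.1 adds an SF-12 analysis to the Final Report, covering "scores collected at baseline, 6 month, 12 month, 2 year, and 3 year visits". It is openly secondary in status: "Though not defined as an objective in the CIP, a posthoc analysis on SF-12 Health Survey scores" is how the section introduces it, and section 3.4.1.1 states that "There is no formal statistical hypothesis associated with this objective".

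The method is in section 3.4.1.3: "Summary statistics (e.g. mean, SD, 95% confidence intervals) and graphical methods will be used to describe SF-12 scores from baseline through 36 months". A physical component score exists only if "all physical health dimension questions must be answered", with the same rule for the mental score. The data rule is "Analysis will be performed on all complete questionnaires from subjects in the mITT dataset".

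The section does not mention change from baseline, a common cohort, a paired interval or a repeated-measures model. Section 3.1.4.2 (Missing Data) confirms an available-case approach without imputation. It also plans a baseline comparison of subjects with complete data and early exits. Section 4.1 gives the expected dropout: "We estimate that the attrition rate will be approximately 10% per year".

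**The concern.** In a single-arm study, a series of quality-of-life means running from before ablation to three years after it will be read as the change that followed treatment. Under the stated data rule, the two ends of that series come from different sets of people. If subjects who leave early had lower scores at the start, the later means rise because of who remains, even if nobody improved.

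The printed intervals do not help a reader who wants to judge change. Each describes the mean at one visit. The same subjects contribute at both visits, so their scores are correlated, and the uncertainty of the difference cannot be obtained from two separate intervals.

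At stake is the interpretation of one descriptive result in the Final Report, not a study success criterion.

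**Working it through.** **Inputs from the SAP.** 370 mITT subjects, 270 followed to 36 months, 10% attrition per year (section 4.1). Five SF-12 visits (section 3.4.1).

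**Assumed inputs.** The SAP gives no SF-12 standard deviation, correlation or dropout profile. I assume SD = 10, a baseline-to-36-month correlation r of 0.4 to 0.7, and a baseline gap of 2 to 5 points between those who stay and those who leave. All questionnaires are taken as complete; incomplete ones would reduce the numbers further.

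**Step 1: reproduce the SAP's attrition figure.** 270 / 0.9³ = 370.4, which agrees with the stated 370. Forward, 370 × 0.9 = 333 at year 1, 370 × 0.9² = 299.7 at year 2 and 370 × 0.9³ = 269.7 at year 3. The share of baseline contributors absent at 36 months is 1 − 0.9³ = 0.271.

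**Step 2: shift from composition alone.** Let C be the baseline mean of those who stay and D that of those who leave. The baseline mean of all subjects is 0.729·C + 0.271·D. If no one's score changes, the 36-month mean is C. The apparent change is then

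C − (0.729·C + 0.271·D) = 0.271·(C − D).

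- Gap of 2 points: 0.271 × 2 = 0.54 points.
- Gap of 5 points: 0.271 × 5 = 1.36 points.
- No gap: zero.
- Leavers healthier at baseline: same size, opposite sign.

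**Step 3: uncertainty of the change.** Three standard errors can be compared.

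- Two visit means treated as independent: 10·√(1/370 + 1/270) = 0.80, a 95% half-width of 1.96 × 0.80 = 1.57 points.
- Difference of the same two visit means, allowing for the 270 being among the 370 and for dropout unrelated to scores: 10·√(1/370 + 1/270 − 2r/370).
- Paired change in the 270 with both scores: 10·√(2(1 − r)/270).

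| r | SE, treated as independent | SE, difference of visit means, overlap allowed for | SE, paired change | Variance ratio, overlap-corrected to paired |
|---|---|---|---|---|
| 0.4 | 0.80 | 0.65 | 0.67 | 0.95 |
| 0.5 | 0.80 | 0.61 | 0.61 | 1.00 |
| 0.6 | 0.80 | 0.56 | 0.54 | 1.07 |
| 0.7 | 0.80 | 0.51 | 0.47 | 1.18 |

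The independent-samples standard error is therefore wrong for change, and too large over this range of r. The visit means themselves carry nearly the same information about change as paired data.

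**The case against.** The strongest defence is that the plan makes no claim about change. The analysis is post hoc, has no hypothesis and sets out to describe scores. A mean, SD and interval at each visit does that correctly, and score levels are a legitimate summary in their own right. The list of statistics is introduced as examples, so change scores are not ruled out. This limits the severity. It does not settle the point, because permitting a change summary is not specifying one, and a series from baseline through 36 months invites the comparison.

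Safeguards exist. Section 3.1.4.2 compares baseline characteristics of completers and early exits, and section 4.2 lists the number of non-missing observations, so shrinkage would be visible. Both could reveal a composition problem. Neither corrects the SF-12 means, and the tipping-point analysis covers only the primary objectives.

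A reader might infer that the plan throws away the precision of paired data, with 1.4 to 2.9 times the variance (0.80² against 0.67² to 0.47² for r = 0.4 to 0.7). The document does not support that. The ratio arises only if someone combines the two printed intervals as though they came from independent samples, and the SAP specifies no such calculation. Once the overlap is allowed for, the ratio is 0.95 to 1.18.

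A reader might also infer that dropout in this study is selective. The SAP contains nothing to show that, and its 10% per year is a planning allowance, not an observed loss.

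Finally, paired change is not a full cure. If subjects leave because they worsen after baseline, those with both scores are still a selected group. That objection stands and shapes the fix.

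**Conclusion.** The point holds as a low-severity improvement. As written, section 3.4.1.3 compares about 370 subjects at baseline with about 270 of the same subjects at 36 months, and gives no estimate or interval for change. Composition alone could move the apparent change by about 0.27 times the baseline gap between stayers and leavers, or 0.5 to 1.4 points for assumed gaps of 2 to 5 points. On an assumed SD of 10, the upper end approaches the 1.57-point half-width a reader would get from two separate visit means. The size and direction rest wholly on the assumed gap; the 27% rests on the SAP's planning attrition. Visit-wise intervals are valid for each visit's mean among those who responded, but not for change. No primary result or sample size is affected.

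**What to change.** In section 3.4.1.3:

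1. Keep the visit-wise means, SDs and intervals as description, with n at each visit.
2. Add within-subject change from baseline at 6, 12, 24 and 36 months, with n and 95% CI, in subjects with both scores. State that this summary speaks only for subjects who remain.
3. Add a repeated-measures mixed model with visit as a factor, using all available scores, and state that it is valid under missing at random.

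The same edit can correct the scoring sentence in that section, which is worded as if there were two time points although five are planned.

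The cost is a few lines of SAP text and code on data already planned for collection. The downside is a missing-at-random assumption that cannot be verified, in an analysis that stays post hoc and descriptive.

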## 4 APPENDIX

### 4.1 Overall Sample Size

In order to adequately power for both the primary effectiveness and safety hypotheses, we require a sample size of 270 evaluable subjects to complete 36 months of follow-up. We estimate that the attrition rate will be approximately 10% per year for the duration of the originally intended 5 year follow-up period. Therefore, the final sample size required to achieve 270 subjects followed for 36 months and account for attrition (i.e. 10% per year) is 370 mITT subjects with procedure attempts. It is expected up to 400 subjects will need to be enrolled to ensure 370 mITT subjects with procedure attempts assuming a small number of subjects who are enrolled will not undergo a procedure.

### 4.2 General Statistical Considerations

All analyses will be performed using SAS statistical software (SAS Institute Inc, Cary, NC). It is planned that the data from all centers that participate in this protocol will be combined for analysis. Descriptive statistics includes but is limited to number of non-missing observations, mean, standard deviation, median, minimum, and maximum for continuous

variables and count and percentage for categorical variables. Unless otherwise specified, the analysis will be performed using descriptive statistics.

### 4.3 Interim Subject Safety Monitoring

No formal interim analyses are planned. However, accumulating data for the safety endpoints may be analyzed at any time per regulatory agency's request. Hypothesis statistical testing will not be conducted until the final analysis. No alpha adjustment will be applied in terms of the analysis of the final primary endpoint for all subjects.

Note that incidence rate estimates from analyses for the interim reports may have some upward bias since subjects that recently had a 36-month visit that occurred prior to precisely 36 months will not be part of the risk set (denominator) at 36 months due to being censored at their last followup.

### 4.4 Sensitivity Analyses

In the rare instance where a subject who has an Ablation Catheter System treated but does not meet all inclusion and exclusion, the subject will not be included in ITT and mITT set. If deemed necessary, analyses performed on the mITT analysis set may be repeated based on all treated analysis set to assess sensitivity to the inclusion/exclusion criteria.

### 4.5 Acronyms

AE	adverse event(s)
AEAC	Adverse Event Adjudication Committee
AF	atrial fibrillation
AFD	atrial fibrillation drug(s)
CI	confidence interval
CIP	Clinical Investigation Plan (protocol)
CPE	cryoablation procedure event(s)
CRF	case report form(s)
CT	computed tomography
CTF	chronic treatment failure
ECG	electrocardiogram
EP	electrophysiology
FDA	Food and Drug Administration
ITT	Intent to Treat population
MAFE	major atrial fibrillation event(s)
MedDRA	Medical Dictionary for Regulatory Activities
MI	myocardial infarction
mITT	Modified Intent to Treat population
MRI	magnetic resonance imaging
PAF	paroxysmal atrial fibrillation
PV	pulmonary vein(s)
RF	radio frequency
SAE	serious adverse event(s)
SAP	statistical analysis plan
SAS	Statistical Analysis Systems (software)
SSED	Summary of Safety and Effectiveness Data

STOP -AF Previous pivotal trial  
 UADE unanticipated adverse device effect(s)

**5 VERSION HISTORY**

Version	Summary of Changes	Author(s)/Title
1.0	
 
Not Applicable, New Document
 
	[name]
2.0	
 
Replaced assessments scheduled to take place at 5 years to reflect new 3 year timeline of the study replaced 5-year outcomes with equivalent 3-year outcomes.
 
Modified the statistical methods for center pooling to accommodate 20- 30 sites (replaced chi square test with Cochran's Q).
 
Specified details about conducting the tipping point analysis
 
Removed language pertaining to describing subject screening
 
Removed additional objectives 1 and 2, which centered around comparing results between this study and the STOP AF Pivotal study, and are now considered out of scope.
 
Specified an additional analysis describing SF-12 scores at baseline, six months, and at year 1, 2, and 3
 
	[name]
